3.4.6 Other Forms

- The **Off-Protocol Form** will be completed by the study coordinator to report deviation(s) from study protocol (e.g., missed visit, incomplete data collection).
- An **Inactivation Form** will be utilized to report patient drop-outs or inactivations and reason(s) for dropping out or inactivation.
- An **Enrollment Form** will be completed to report those participants who are enrolled into LABS-3 Psychosocial. This form reports whether patients provided consent to LABS-3 Psychosocial, along with dates of consent. If the patient does not consent, the reason why is reported.

4 Data Analysis and Statistical Power

Statistical Analyses

1. Preliminary Analysis
 - a. Descriptive Statistics. Descriptive statistics (e.g., means, standard deviations, ranges, frequency distributions) at each assessment point will be performed on all demographic,

psychopathology (SCID-I, BDI), eating behavior (EDE-BSV, NDS) and quality of life (SF-36, IWQOL-Lite) measures.

b. Site Comparisons. Baseline comparisons between sites will be made on demographic, psychopathology, eating behavior and quality of life measures using ANOVA for continuously distributed measures, Kruskal-Wallis for ordinal or continuous non-normal measures, and chi-square tests for nominal measures.

c. Missing Data Analysis. A pattern mixture model (Little, 1993; 1994; 1995; Hedeker & Gibbons, 1997) based on a random regression model (RRM) (Gibbons, et al., 1993) will be used to examine the impact of missing data pattern on longitudinal eating-related variables, weight loss, quality of life, and depressive symptomatology. Subjects will be divided logically into groups based on their missing data pattern following the guidelines provided by Hedeker & Gibbons (1997). These groups will then be included as a between-subjects factor and the impact of this factor on the trajectory of outcome measures will be evaluated. This will provide a determination of the extent to which trajectories depend on the pattern of missing data.

2. Hypothesis Testing

a. Hypothesis #1. Hypothesis #1 posits that patients undergoing bariatric surgery will experience significant decreases in rates of psychopathology and quality of life. This hypothesis will be evaluated using a linear RRM (Gibbons, et al., 1988; Gibbons, et al., 1993; Bock, 1983) for depression (BDI total score) and quality of life (IWQOL-Lite total, SF-36 mental and physical component). A logistic RRM (Stiratelli, et al., 1984) will be used for psychopathology (current mood disorder, current anxiety disorder, current substance use disorder). All of the basic models will include a random effect for subject, and fixed effects for site, assessment time, and time-by-site interaction. Additional variables may include relevant covariates and missing data patterns. Bonferroni contrasts will be used to compare mean scores (for depression and quality of life) or rates of psychopathology between pre-surgical and subsequent assessment points. Analyses will include data from all participants completing at least one post-surgery assessment.

b. Hypothesis #2. Hypothesis #2 states that untreated psychopathology that persists beyond surgery will be associated with less weight loss and poorer quality of life. The effects of post-surgical psychopathology upon weight loss and quality of life will be evaluated using linear RRM's. The basic models will include a random effect for subject, fixed effects for baseline assessment, assessment time, and time-varying covariates for psychopathology (current mood disorder, current anxiety disorder, current substance use disorder, any Axis I disorder). The main effect for assessment time will be used to evaluate within-person change. The use of time-varying covariates for psychopathology allows for the possibility that a given diagnosis may be present for a given subject at one time point but absent at another. Outcome measures for these analyses for weight loss will be BMI, and for quality of life will include the IWQOL-Lite total and SF-36 mental and physical components.

c. Hypothesis #3. Hypothesis #3 states that untreated psychopathology at the time of bariatric surgery will be associated with increased short-term complications. A logistic regression analysis will be used to evaluate the influence of psychopathology at the time of surgery on short-term surgical complications. Analyses will evaluate the impact upon both DSM-IV diagnostic psychopathology (e.g., current mood disorder, current anxiety disorder, current substance use disorder, any Axis I disorder, any Axis II disorder) and a continuous measure of depressive symptoms, the BDI, upon short-term post-surgical complications.

d. Hypothesis #4. Hypothesis #4 posits that syndromal or subsyndromal eating disorders prior to surgery will be associated a greater frequency of eating disorder symptoms and less weight loss at long-term follow-up. Data from the EDE-BSV and the NDS dietary recall will be aggregated to determine the frequency of various eating disorder symptoms (binge eating, grazing, vomiting, chewing and spitting) at each assessment point. RRM's will then be used to evaluate the effect of pre-surgical eating disorder syndromes (including binge eating disorder and night eating) on eating disorder frequency (Poisson-based RRM) and BMI (linear RRM). The basic models will include a random effect for subject, and fixed effects for site, assessment time, time-by-site interaction, and pre-surgical eating disorder diagnoses (both syndromal and subsyndromal diagnoses).

Power Analysis and Sample Size

Hypothesis #1. Power analyses below assume an attrition rate of 15% at 12 months, and a 10% attrition rate at 24 month assessments. An enrolled sample size of 250 would provide an estimated sample size of 213 at 12 months and 191 at 24 months.

Power analyses regarding the reduction of psychopathology following surgery is based on the finding of Glinski et al. (2001) that 50% of pre-bariatric surgery candidates meet criteria for at least one current Axis I disorder. Assuming a conservative two-tailed alpha of .01, the proposed sample size would provide a power of .90 to detect a reduction in psychopathology of just over 10% from pre-surgery at 12 months and 12% at 24 months (Hintze, 2001). These reductions for Axis I disorders are consistent with those reported in the literature following bariatric surgery (Herpetz et al. 2004).

Effect size estimates for changes in quality of life and depression scores after post-surgery are taken from the Utah Obesity Surgery Study (Adams et al., 2005). A total of 224 bariatric surgery patients were evaluated using the IWQOL-Lite and SF-36 prior to surgery and at 1-year follow-up. The IWQOL-Lite total score improved from 32.4 ± 16.1 pre-surgery to 86.6 ± 16.1 at 1-year follow-up (effect size = 3.37); the SF-36 mental component, which is highly correlated with measures of depression, improved from 41.1 ± 6.4 pre-surgery to 44.8 ± 6.4 at 1-year follow-up (effect size = .58); the SF-36 physical component improved from 35.4 ± 6.5 pre-surgery to 45.2 ± 5.8 at 1-year follow-up (effect size = 1.51). Power estimates assume a conservative two-tailed alpha of .01, a correlation between pre-surgical and follow-up assessments of .50, and differences between pre-surgical and post-surgical assessments in quality of life and depression comparable to those from the Utah study. The proposed sample size would provide a power of greater than .98 to detect these differences between pre-surgical and subsequent post-surgical assessments quality of life and depression scores at each follow-up assessment (Hintze, 2001).

Hypothesis #2. Power analyses for Hypothesis #2 are based upon a study by Averbukh et al. (2003) reporting a correlation between pre-surgical BDI score and subsequent weight loss of .397, corresponding to an effect size (d) of .64 (Cohen, 1988; p. 82). Power analysis for this hypothesis is based upon the procedures described by Hedeker and colleagues (Hedeker, et al., 1999) for longitudinal random effects models with attrition. Power analyses assume a conservative two-tailed alpha of .01, a 50% rate of pre-surgical Axis I disorder, and 4 observation points (6, 12, 18 and 24 months), and a correlation of .30 between observations.

Power analyses focus on the differences weight loss between those individuals with and without pre-surgical psychopathology. The proposed sample size will provide a power of approximately .95 to detect an attrition-adjusted effect size of .64 (Hedeker et al., 1999).

Hypothesis #3. Power analysis estimates for Hypothesis #3 are based upon a study by Powers et al. (1988) reporting an association between the presence of pre-surgery Axis I diagnosis and post-surgical complications. All 9 (100%) patients with a pre-surgical Axis I diagnosis experienced post-surgical complications, compared to 7 of 15 (47%) of those without a pre-surgical Axis I diagnosis (contingency coefficient = .42). It would be unrealistic to expect that every patient with an Axis I disorder would develop post-surgical complications. However, if we assume that 80% of those with an Axis I disorder would develop complications post-surgery, and further assume a conservative two-tailed alpha of .01, the proposed sample size of 250 enrolled patients would provide a power of .98 to detect this association and would provide a power of .80 to detect a contingency coefficient of .165 (Hintze, 2001).

Hypothesis #4. Power analysis for Hypothesis #4 is based upon a study of Hsu et al. (1996) reporting an association between pre-surgical eating disturbance and weight regain post-surgery. They report that 8 of 19 (42%) patients with pre-existing eating disturbance regained weight after surgery, compared to 0 of 5 (0%) without a pre-existing eating disturbance (contingency coefficient = .341), corresponding to an effect size (d) of .57. Power analyses assume a conservative two-tailed alpha of .01, a 50% rate of pre-surgical eating disturbance, and 5 observation points (6, 12, 18 and 24 months), and a correlation of .30 between observations. Power analyses focus on the differences weight loss between those individuals with and without pre-surgical psychopathology. The proposed sample size of 100 subjects for the assessment of eating behavior will provide a power of approximately .88 to detect an attrition-adjusted effect size of .57 (Hedeker et al., 1999).

5 Study Organization

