3.4.2 Interview Description

- Structured Clinical Interview for DSM-IV, Patients Edition (SCID-IP; First, et al., 2001). The SCID-P is a widely used semi-structured interview that will be administered to assess comorbid Axis I disorders. Further, an impulse control module will be administered to assess impulsive/compulsive disorders for participants at their 72 month visit and beyond. A review of reliability studies for the SCID found kappa coefficients (measures of inter-rater reliability) ranging from .03 to 1.00, although the majority of the studies found kappas in the range of .7 to .8; test-retest coefficients ranged from .37 to .89.
- M-FED Bariatric Surgery Version (M-FED-BSV). Data will be obtained on other treatment received using the M-FED, an instrument designed for this purpose that has been used in several multi-center BN treatment and longitudinal studies (See for example, Mitchell, et al., 2002; Crow, et al., 2002). A modified version is available for bariatric surgery patients (M-FED-BSV).
- Eating Disorder Examination (EDE-BSV; Fairburn & Cooper, 2006). The diagnostic version of the EDE will be used as the primary measure of eating behavior and pathology. The EDE is an investigator-administered interview used to assess current eating disorder symptoms. The EDE contains four subscales (Restraint, Eating Concern, Shape Concern, and Weight Concern) associated with core psychopathology of eating disorders, as well as frequency measure of binge eating and compensatory behavior. The

validity and reliability of the EDE have been well documented (Fairburn & Cooper, 1993). We have modified a version of the EDE for use with bariatric surgery patient and this form will be used (EDE-Bariatric Surgery Version, EDE-BSV). The modified version of the EDE quantifies eating behavior, experiences of plugging and dumping syndrome, binge eating, grazing, compensatory behaviors, such as vomiting, and chewing and spitting food. This version includes assessment of night eating and excessive fluid intake. The modified version of the EDE has been used in gathering data on eating behaviors in RYGBP patients in prior studies.

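### Hypothesis 1 is powered on any current Axis I disorder but never tests it, and its 10% and 12% detectable reductions cannot be reproduced from the stated inputs

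*Protocol*

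**What the plan says.** **Analysis (Protocol Section 4, Hypothesis Testing, Hypothesis #1).** The BDI and quality-of-life scores get a linear random regression model (RRM). For diagnoses, a logistic RRM "will be used for psychopathology (current mood disorder, current anxiety disorder, current substance use disorder". The list stops there. The Hypothesis #2 and #3 paragraphs name the same three disorders and add any Axis I disorder.

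**Power (Protocol Section 4, Power Analysis and Sample Size, Hypothesis #1).** The starting point is that "50% of pre-bariatric surgery candidates meet criteria for at least one current Axis I disorder". The text continues: "Assuming a conservative two-tailed alpha of .01, the proposed sample size would provide a power of .90" to detect a reduction of "just over 10% from pre-surgery at 12 months and 12% at 24 months". The sample sizes are 213 and 191, from 250 enrolled. No test is named, and no correlation or discordance is given for this binary outcome. The next paragraph, on the score outcomes, assumes "a correlation between pre-surgical and follow-up assessments of .50".

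**Schedule (Protocol Section 3.4.1).** Both visit tables mark the SCID before surgery and then at annual follow-up, which the second table starts at 2 years. Neither marks it at 12 months. Section 3.4.2 adds that "an impulse control module will be administered to assess impulsive/compulsive disorders for participants at their 72 month visit and beyond".

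**The concern.** The outcome that carries the power claim should be among the outcomes analysed. Here it is not, so the protocol's only assurance about detecting a fall in diagnosed psychopathology attaches to an endpoint that Hypothesis 1 never tests. The three disorders that are tested are each part of Axis I, so none can be more common than the composite. The protocol gives no current rate for any of them in this population, so their power cannot be judged.

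The power claim itself also matters. If the study is less sensitive than stated, a non-significant change in diagnosis rates could be read as evidence of no change when the design could not reliably detect one of that size. Finally, a detectable reduction at 12 months means little if no diagnostic interview is scheduled then.

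**Working it through.** **Inputs.** Baseline rate .50, two-sided alpha .01 (z = 2.576), power .90, 250 enrolled, attrition 15% and then 10%: all from the Hypothesis #1 power text. The reductions are read as absolute points. The correlation for the binary outcome is not stated, so it is varied.

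**1. Sample sizes.** 250 × .85 = 212.5, and 212.5 × .90 = 191.25. The stated 213 and 191 reproduce.

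**2. Formulas**, with p1 = .50, p2 = .50 − d, q = 1 − p, p̄ the mean of p1 and p2, and φ the within-person correlation:
- One-sample test against 50%: power = Φ[(d√n − z√.25) / √(p2·q2)].
- Independent proportions: power = Φ[(d√n − z√(2·p̄·q̄)) / √(p1·q1 + p2·q2)].
- Paired McNemar: power = Φ[(d√n − z√ψ) / √(ψ − d²)]. Here ψ = p1 + p2 − 2·p11 is the total discordance, and p11 = p1·p2 + φ√(p1·q1·p2·q2).

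**3. Worked example, n = 191, d = .12.** d√n = 1.658.
- One-sample: (1.658 − 1.288)/.485 = .76, power .78.
- McNemar, φ = .50: p11 = .190 + .50 × .2427 = .311, ψ = .257. Then (1.658 − 1.307)/.493 = .71, power .76.
- McNemar, φ = .65: p11 = .348, ψ = .184. Then (1.658 − 1.106)/.412 = 1.34, power .91. The exact test also gives .91.

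**4. Smallest reduction with power .90 at two-sided alpha .01 (points).**

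| Test | 12 months, n = 213 | 24 months, n = 191 |
|---|---|---|
| Stated in the protocol | just over 10 | 12 |
| One-sample | 13.1 | 13.8 |
| Independent proportions | 18.3 | 19.2 |
| McNemar, φ = .30 | 15.6 | 16.5 |
| McNemar, φ = .50 | 13.3 | 14.1 |
| McNemar, φ = .60 | 11.9 | 12.6 |
| McNemar, φ = .65 | 11.2 | 11.8 |
| McNemar, φ = .70 | 10.4 | 11.0 |

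**5. Power at the stated reductions, same alpha.**

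| Case | One-sample | Independent | McNemar φ = .50 | McNemar φ = .65 | McNemar φ = .70 |
|---|---|---|---|---|---|
| n = 213, 10 points | .64 | .31 | .63 | .81 | .87 |
| n = 213, 11 points | .74 | .39 | .73 | .89 | .94 |
| n = 191, 12 points | .78 | .42 | .76 | .91 | .95 |

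Power of .90 requires total discordance of no more than about .147 for 10 points and .177 for 11 points at n = 213, and .190 for 12 points at n = 191.

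**6. Relative reading.** If 10% and 12% meant relative falls (50% to 45%, and 50% to 44%), power would be only .13 to .24 and .18 to .32 across the one-sample test and McNemar with φ of .50 and .70. The absolute reading is the more favourable one.

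**7. Other correlations in the protocol.** It assumes .50 for the Hypothesis 1 scores, and .30 between repeated observations for Hypotheses 2 and 4. The .65 to .70 needed here is above both.

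**The case against.** The strongest reply is that the stated figures are attainable. The power text gives no correlation for the diagnosis outcome. The .50 belongs to the quality-of-life and depression scores, and the protocol sets its correlations analysis by analysis. A paired test at two-sided alpha .01 does reach about .90 when φ is .65 to .70. Such values are possible: with a 50% baseline and 38% at follow-up, the largest possible φ is (.38 − .19)/.2427 = .78. At φ = .65 about 15% of the sample would remit and 3% would be new cases. This stands. A reader might infer that the 10% and 12% figures are false at alpha .01, but the documents support only that they rest on an undeclared and comparatively high correlation.

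A reader might also infer that the calculation was run at alpha .05, because φ = .50 then gives 11.1 and 11.8 points and a one-sample test gives 11.0 and 11.6. The match is close, but a higher correlation at alpha .01 also fits, and the protocol cannot separate the two.

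Nor can one say that the tested disorders are too rare to fall by 12 points, since the protocol gives no current rate for them.

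On the schedule, Section 3.4 describes complete follow-up at about 12 months, which could be taken to include the SCID. But 12 months has its own column in both tables, and neither marks the SCID there. The two places need reconciling.

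None of this answers the endpoint mismatch. The Hypothesis 1 list is closed, and the composite is named in the next two hypotheses.

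**Conclusion.** The mismatch is plain from the text and rests on no assumption: Hypothesis 1 claims power for any current Axis I disorder and tests three narrower diagnoses that have no stated rate or power.

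The detectable reductions cannot be reproduced from what the protocol states. Under a one-sample test, or a paired test with an assumed correlation of .50, they are about 13 points at 12 months and 14 at 24 months. Power at the stated reductions is then about .63 to .74 (10 to 11 points) and .76 to .78 (12 points), against the claimed .90. Independent proportions do worse. The stated values need a correlation of about .65 to .70. These results assume a 50% baseline, absolute reductions and a simple pre/post comparison.

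The 12-month figure has no scheduled diagnostic interview behind it in either table. The point does not touch the Hypothesis 1 score outcomes, which have their own power statement. It should be corrected, and it does not invalidate the design.

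**What to change.** 1. Add any current Axis I disorder as a logistic RRM outcome for Hypothesis 1. Build it only from the SCID modules used at baseline and at every SCID visit, and leave out the impulse-control module that starts at 72 months, so that late rates do not rise merely because more is asked.
2. In the power text, name the test, state the assumed within-person correlation or discordance, and say that the reduction is in absolute points.
3. Restate the 24-month detectable reduction to match: about 14 points at two-sided alpha .01 if the correlation is .50, and about 12 only if it is about .65.
4. Drop the 12-month diagnosis figure, or reconcile it with the SCID schedule in Section 3.4.1.

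The cost is one more model, some rewording and a less favourable stated figure. No change to enrolment is needed.

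### Hypothesis 1 leaves out participants with no post-surgery assessment although the planned models can use their baseline data; this discards collected data and may bias the pre-surgery reference if those participants differ at baseline

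*Protocol*

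**What the plan says.** The Hypothesis #1 paragraph of protocol section 4 plans a linear random regression model for the BDI, IWQOL-Lite and SF-36 scores and a logistic one for current mood, anxiety and substance use disorders. The structure is: "All of the basic models will include a random effect for subject, and fixed effects for site, assessment time, and time-by-site interaction". Bonferroni contrasts then compare mean scores or "rates of psychopathology between pre-surgical and subsequent assessment points". The paragraph ends with the analysis set: "Analyses will include data from all participants completing at least one post-surgery assessment". It gives no reason for this limit.

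Missing data are handled in two other places. The preliminary Missing Data Analysis (section 4, item 1c) is a pattern-mixture model: "Subjects will be divided logically into groups based on their missing data pattern", and then "These groups will then be included as a between-subjects factor and the impact of this factor on the trajectory of outcome measures will be evaluated". That item states no minimum follow-up. In the Hypothesis 1 models the pattern terms are optional: "Additional variables may include relevant covariates and missing data patterns".

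The power section for Hypothesis 1 states: "Power analyses below assume an attrition rate of 15% at 12 months, and a 10% attrition rate at 24 month assessments". The protocol does not say how many participants it expects to have no post-surgery assessment at all, or whether they would differ at baseline.

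**The concern.** A random regression model fitted by likelihood accepts subjects with a single observation. A participant seen only before surgery still informs the pre-surgical mean or rate and, through the within-person correlation, the follow-up estimate. Requiring one follow-up is therefore unnecessary. It also selects the analysis set on something that happens after baseline.

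The pre-surgical value is the reference in every Hypothesis 1 contrast, and the hypothesis concerns people who have surgery, not only those who come back. If those lost before any follow-up have more psychopathology than the rest, the analysed baseline is too healthy and the estimated change describes returners.

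**Working it through.** **Inputs from protocol section 4**
- 250 enrolled; attrition 15% at 12 months and a further 10% at 24 months.
- Current Axis I disorder at baseline: 50%. Detectable reduction: just over 10 points at 12 months and 12 points at 24 months.
- SF-36 mental component: 41.1 to 44.8, SD 6.4, so a change of 3.7.
- Correlation between pre-surgical and follow-up scores: .50 (stated for the continuous outcomes).
- Two-tailed alpha .01.

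**Assumptions, not in the protocol**
- Share never returning, s: 5% to 15%. The top value means that nobody lost by 12 months had an earlier visit.
- Baseline disorder rate among them, p: 55% to 70%.
- For the SF-36, a baseline difference from the remaining participants of 0 to 1 SD.
- For the disorder rate, a correlation of .50.

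**Step 1. The plan's own figures.** 250 × 0.85 = 212.5 (stated 213). 250 × 0.85 × 0.90 = 191.25 (stated 191). A paired t-test on the SF-36 mental component has power above .999 at both sizes, consistent with the stated value above .98. At the 15% ceiling, about 37 of 250 baseline records would be discarded.

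**Step 2. Shift in the baseline rate.** Analysed baseline = (0.50 − s·p) / (1 − s).

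| s | p | Analysed baseline | Shift (points) |
|---|---|---|---|
| 5% | 55% | (0.50 − 0.0275)/0.95 = 49.7% | 0.3 |
| 10% | 65% | (0.50 − 0.065)/0.90 = 48.3% | 1.7 |
| 15% | 65% | (0.50 − 0.0975)/0.85 = 47.4% | 2.6 |
| 15% | 70% | (0.50 − 0.105)/0.85 = 46.5% | 3.5 |

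**Step 3. Shift in the change, which is what is tested.** When loss depends only on baseline, the retained group's follow-up value moves with its baseline. The bias in the change is then about (1 − r) × the baseline shift. With r = .50, 0.3 to 3.5 points at baseline become about 0.15 to 1.8 points in the change. If sicker people leave, the reduction is understated.

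**Step 4. SF-36 mental component.** Bias = −(1 − r) × s × difference × SD.
- No difference: 0.
- s = 5%, 0.25 SD: −0.5 × 0.05 × 0.25 × 6.4 = −0.04.
- s = 15%, 1 SD: −0.5 × 0.15 × 1 × 6.4 = −0.48, on a change of 3.7.

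**Step 5. Exclusion against inclusion by simulation.** Two time points, n = 250, 15% baseline-only, 10,000 runs, true baseline 41.10 and true change 3.70. Inclusion uses the likelihood estimate: the follow-up mean of returners, adjusted by the regression on baseline to the mean of everyone.

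| Loss mechanism | Exclude: baseline, change (SE) | Include: baseline, change (SE) |
|---|---|---|
| Unrelated to baseline | 41.10, 3.70 (0.435) | 41.10, 3.70 (0.426) |
| Odds × 1.5 per SD lower | 41.48, 3.50 (0.435) | 41.11, 3.69 (0.427) |
| Odds × 2.5 per SD lower | 41.90, 3.30 (0.435) | 41.10, 3.69 (0.434) |

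With loss unrelated to baseline, 0.435/0.426 = 1.02, so exclusion costs about 2% in standard error. With loss dependent on baseline, inclusion removes nearly all of the bias.

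**The case against.** The strongest defence is that the rule is mild. It is not a complete-case rule, because anyone with partial follow-up stays in. Sections 3.4 and 3.4.1 offer nine scheduled assessments (6, 12, 18 and 24 months, then years 3 to 7), allow telephone assessment and draw several self-report measures from LABS-2. The share with no follow-up at all may therefore be well below 15%. This stands, and it is why 15% is a ceiling here.

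Four stronger readings are tempting, and the protocol does not support them.
- **That the reference is biased.** Bias needs never-returners to differ at baseline, and nothing in the protocol shows this.
- **That up to 3.5 points should be set against the planned 10 to 12 point reduction.** The first is a shift in the baseline rate, the second a change. The comparable figure is about half as large and, if sicker people leave, works against the hypothesis.
- **That the rule removes the most extreme drop-out pattern from the pattern-mixture check.** Item 1c is a separate preliminary analysis without this restriction, and so are the descriptive statistics. The narrower point holds: within the Hypothesis 1 models, a baseline-only pattern cannot occur.
- **That the logistic models lose up to 59 people (250 − 191).** The year-by-year schedule has no SCID between surgery and 2 years, so this follows only if the rule means the modelled outcome rather than any assessment. The text does not say which, and some participants may return after year 2.

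**Conclusion.** The rule is unnecessary for the models chosen and discards pre-surgical data already collected. That part rests on the text alone. Bias is conditional: it may arise if people lost before any follow-up differ at baseline.

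Under the assumed shares and rates, the effect is modest: up to 3.5 points in the baseline disorder rate, about 1.8 points in its change, and about 0.5 points of 3.7 on the SF-36 mental component. The direction is towards understating improvement if sicker people leave, and the reverse if healthier people do. If the groups do not differ, only about 2% in standard error is lost. The stated power for the continuous outcomes is safe either way.

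Inclusion did no worse than exclusion in any case simulated, though its protection relies on loss being explained by observed data. This is a free improvement of low to moderate severity.

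**What to change.** Replace the last sentence of the Hypothesis #1 paragraph with: *Analyses will include all participants who underwent bariatric surgery and have a baseline or at least one post-surgery assessment; those with no follow-up contribute their baseline data under the missing-at-random likelihood.*

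The surgery condition matters. Consent and the baseline visit come 1 to 30 days before the operation, so admitting everyone enrolled with a baseline would bring in people who never had surgery, to whom the hypothesis does not apply.

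Keep the at-least-one-follow-up set as a sensitivity analysis, and say whether an assessment there means any visit or the outcome being modelled. In item 1c, compare baseline-only participants with the rest at baseline, or merge them with the earliest drop-out group. A group with one time point has no trajectory that can be estimated separately without further identifying restrictions.

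The cost is one replaced sentence, a line in item 1c and one sensitivity run. No new data are needed.
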